Old SCHOOL Hip-Hop: Improve Alzheimer's Disease Knowledge

NCT03284112 Last Approved Date: April 16, 2025

[figure not shown]
RESEARCH METHODS

6.1. Phase 1: Program Refinement. The first 6 months of the project period will focus on generating a larger item pool using focus groups and cognitive interviews. These items will be administered during the study in order to provide data for future/further development of outcome measures for AD recognition. Additionally, items to measure self-efficacy and other constructs relevant to the study goals will be added and examined in relation to the outcome; these will comprise a novel "dementia action test" (See Section 6.5.1.). Concomitantly, a 3-minute program cartoon will be developed, mapped to our song, comics, and character icons focusing on the FLOW mnemonic and primary behavioral outcomes; these products were created in advance of this application. **6.2. Phase 2: OSHH Randomized Controlled Trial**

6.2.1. Study Design. We will use a cluster randomized controlled trial (RCT) design with random assignment of

10 schools to each of two arms: control and intervention (Figure 4). The data coordinating center has developed randomization algorithms for rollina enrollment as schools will be contacted on a rolling basis over the 5 year study period. Outcome measures are (1) Child's recall of dementia symptoms (at 3 days and 3 months follow-up), (2) parent's report of whether the child communicated the information (at 1-week follow-up) and (3) parent's recall of the symptoms and response (at 1-wk and 3-m follow-up).

6.2.2. Population. 4th and 5th grade children (ages 9-11y), and their parents (age > 20 years), in selected NYC public schools with similar sociodemographic composition. **Exclusion criteria**. Schools

having already received pilot OSHH and HHS programming.

- **6.2.3. Recruitment and Retention.** School Principals identified by School District Superintendents, Department of Education Health Directors, and local relationships, will be contacted by phone. A meeting will be scheduled with research staff and the school principal to show a specially- developed 10-minute explanatory video that shows the OSHH curriculum and program objectives; and questions about the program will be answered. Once the principal has agreed for his/her school to participate, research staff will work with parent coordinators to identify 4th and 5th grade students and their parents from school rosters. Parents will be recruited in-person at school events and/or by telephone. Informed consent from parents will be obtained for the enrollment of their child and themselves in the study. Assent will be obtained from each participating child. Based on our pilot study we estimate that 35% of parents will refuse to participate. Parents and students are informed that testing will have no impact on grades or school relations.
- **6.2.4. Alternative recruitment strategy.** In clinical trials, recruitment often becomes a problem because if the researchers have overestimated their ability to recruit at a particular site, they must have a plan to open up additional sites. That is not a relevant concern here. Once the school has agreed to serve as a site, we will include all the children in the 4th and 5th grades. If, for any reason, one or more children choose (or their parents choose) not to participate, or if the child missed school on any or all of the days on which the program was being implemented, this would not indicate a need to recruit "replacements", nor would it affect our statistical power, which is calculated using the school, not the child, as the unit of analysis.

6.3.1. Old SCHOOL Hip Hop Intervention. Hip-hop is a music genre that strongly emphasizes rhyme and dance, and is popular among diverse socioeconomic and ethnic groups.⁴⁶ Integrated rhyme and dance have been successful educational tools in non-health oriented education programs. 47-49 Hip-hop has specifically been used as a vehicle for obesity prevention in African-American preschoolers⁵⁰ as well as in our stroke education model. 1, 3, 4 Guided by an interdisciplinary team which included school principals, school-aged children with whom focus groups and semi-structured interviews were conducted, public health experts, children's education television/media experts (formerly of Sesame Street), hip hop artists, bio-behavioral researchers and clinical dementia experts, we developed our OSHH program using community engagement techniques.

In the course of project development, we were particularly mindful of the potential for introducing undue distress on these children by burdening them with the responsibility of being arbiters of family dementia knowledge. We specifically reviewed these concerns with the focus group and engaged a child psychologist, both of whom identified stroke as likely more burdensome given its immediate, urgent, and physically apparent presentations. However, due to the Entertainment Education framework of our intervention, which includes the use of the hero concept (making stroke communication to parents a potentially life-saving heroic act), we had no such adverse outcomes in the 5 year experience with our related Hip Hop Stroke (HHS) program (Section 5.1).

modular 1 hour/day for 3 days school-based multi-media dementia educational program designed to increase dementia literacy among 4th and 5th grade children, and to motivate them to deliver the message to their families and adult caregivers with the aid of homework activities OSHH uses

Day 1: 60 minutes

Introduction to dementia

2. Unprompted pre-test

Pre-test and

2. Content:

networks

Section 6.5.1.b)

learning's w/parents

Topic

[figure not shown]
Content

The final intervention is a Figure 5. OSHH comic book excerpt distributed at the program, reviewing the "FLOW" mnemonic and examples of normal versus pathologic cognitive aging

[figure not shown]
LOSE their way getting

to familiar places.

LOSE interest.

Forgets all the time Gets lost going to regular places by herself, like

things she used to do. such as going to church

culturally and age-appropriate music, role-play skits, and short animated films as motivating tools to enhance a simple didactic program delivered over three days (See **Table 1**). Students are educated using interactive play, cartoons, and an original song featuring an ADthemed rap. For the development of a mnemonic novel to this program, we reviewed validated concepts of AD relevant to public health awareness including the Alzheimer Disease Knowledge Scale, 42 the

Alzheimer's Association's "Know the 10 Signs," 51 as well as extensive clinical experience of the investigators. Through our experience with the HHS program, we found that six to seven key disease knowledge elements could be reasonably included in a combination of mnemonic and simple related messaging and retained for a prolonged period of time.^{1, 3} As such, our group devised the "F.L.O.W." mnemonic (Forget, Lose, **O**verlook, **W**rite/**W**ander), which captures many of the cardinal symptoms of AD, including Forgetting conversations, words, people/names, or dates, **L**osing objects, one's way (direction), or interest, **O**verlooking bills, hygiene, household cleanliness, or safety, and increasing reliance upon **W**ritten lists or **W**andering away from the family. In addition, we include key AD educational elements of localization (that AD occurs in the brain, areas specific to memory, and the hippocampus). We also review additional AD symptoms of executive dysfunction through role play.

In response to recognizing a patient with possible AD, we teach students to "Go With The FLOW" – a call to action that includes bringing AD symptoms to the attention of unaffected adults in the family unit, encouraging medical evaluation, and using methods to improve the household safety of a person with AD. With each AD symptom, we provide comparisons with normal aging, intending to improve the sensitivity of AD symptom recognition (and lowering the false negative fraction of symptom recognition), while also focusing on deceasing the false positive symptom identification (and thus increasing specificity); we emphasize that in normal cognitive aging, symptoms occur "once in a while," whereas AD symptoms are more consistently present, occurring "all the time." The FLOW mnemonic reinforces key symptoms. Two contrasting adult characters: "Ima Good" (normal cognitive aging) and "Anita Help" (concerning for AD) are introduced to emphasize these points (Figure 5). After reviewing each profile, students are asked to decide if the characters are experiencing normal aging or if one "might have the FLOW" (AD). The intervention also involves behavioral engagement, with role-play of AD symptoms and communication of the AD-related information to an adult. AD concepts are introduced in a comic book (Figure 5; See Supplemental File: Comic) which is distributed during the program and made available on our website along with the program's song "Go With The FLOW." Grouped by grade, the students will be educated within school auditoriums. The educational team will be comprised of two facilitators developed and monitored as described in Section 6.4.b. Each child will be given a hand-held audience response system and an ID card with a unique 4-digit identifier – a data collection method we have used successfully in our prior studies.⁵² Children will be instructed to enter the ID number during each test (See Section 6.4.b.).

3-month booster session: After 3 months, an unprompted posttest will be administered to *assess retained knowledge from the program*. This post-test will be followed by a brief OSHH booster session. **Table 1** reviews the curriculum for that date as well.

- **6.3.2.** Attentional control condition: My Pyramid in Egypt. The program selected for the control arm, "My Pyramid in Egypt," will address nutrition, physical activity and obesity education. This program was selected because nutrition, physical activity and wellness programs are now being incorporated into New York City public school curriculums as part of a legislative directive. The New York State "Healthy Schools Act" of 2007 requires school districts to establish "School Wellness Policies" that include a nutrition education curriculum and physical activity. Trained facilitators will conduct "My Pyramid in Egypt" using Egyptian history as an entry point for the USDA's MyPyramid nutrition program. Students will learn about MyPyramid and MyPlate across the 3-day one-hour-a-day program. The educators will be shown an edited music video for Michael Jackson's Egyptian-themed video "Remember the Time." Similar to the intervention, control children will be provided with a take-home activity sheet on Day 1 to complete. Parallel pre and post-tests will be conducted with the control children, using the same test sequence as the intervention. Three months later, students will be assembled by program facilitators for an unprompted, post-test and booster "My Pyramid in Egypt" session to mirror intervention procedures.
- **6.4.a. Data tracking.** An innovative aspect to the conduct of the trial is our use of an audience response system that allows us to track individual children's' test scores throughout the trial period.⁵² The system uses a handheld electronic wireless keypad which engages and excites children all of whom have grown up in the digital age. Each child is assigned a unique ID, entered via the keypad; and the children use the keypad to enter information, including their answers to probe questions (to assess learning and retention). The questions themselves are presented to the group by projecting them onto a large screen. This system allows us to easily keep track of real-time test results that are stored for subsequent analysis, for a large volume of participants, without the expense and transcription errors of manual data entry.
- **6.4.b. Program Fidelity.** Program content will be standardized through a digitized, standardized curriculum (digital slide-show) and educator performance will be measured against a program standard (See Supplemental File: **Evaluator Assessment Form).** Our training program was designed for Lay Health Educators to facilitate scalability. Our Lay Health Educators having already delivered our pilot studies will be prioritized to deliver this program; their performance during the pilot program was filmed and establishes the program standard. Each additional/new Lay Health Educator will watch that performance, learn the new curriculum, and co-teach the program with one of our senior educators prior to independent facilitation. Any new educator must meet set standards for independent work prior to initiation. Research staff will thereafter perform biannual fidelity activities on program delivery to ensure compliance with OSHH protocols and procedures. Qualitative assessments of

performance will be done through videotaped performances that will be reviewed by research staff in conjunction with the educators. Educators will complete a self-assessment (See Supplemental File: Self-Assessment Form) in advance of being provided feedback on specific and remediable aspects of performance to meet consistent standards. Educators not meeting expected standards will be provided remediation and tracked at their subsequent performance. Two successive performances below expectations will require the educator to be formally retrained and will not be able to teach independently until meeting expectations. Quantitative assessments of educator and program performance will measured in real-time using outcomes tracked by the audience response system and linked with the qualitative observations. We will also track the use of our online program portal by participants and benchmark this access so that we can monitor it for outliers.

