6.5. Procedures

- **6.5.1.a. Item pool generation.** Focus groups and cognitive interviews will refine item generation of the planned "dementia action test" relating key FLOW items with hypothetical scenarios and expressed behavioral intent. Included will be measures demonstrating self-efficacy and attitudes, including relevant elements of the Dementia Attitudes Scale⁵³
- **6.5.1.b.** "Go With the FLOW" Cartoon development. A 3-minute program cartoon similar in style to our Hip Hop Stroke cartoons¹ will be developed and mapped to our existent song of the same title (See Supplemental File: Lyrics), related comics, and character icons (see **Figure 5**) focusing on the FLOW mnemonic and primary behavioral outcomes.
- **6.5.1.c.** School selection/recruitment. The Office of School Wellness of the New York City Department of Education and local school district Superintendents will collaborate with Investigators to identify NYC schools with similar demographics, excluding schools having already participated in our programs. School Principals will be invited to participate in the research study during face-to-face presentations of the intervention and control programs. During this meeting, a specially developed 10-minute explanatory promotional video will explain the OSHH intervention and show the curriculum and program objectives, and guestions will be answered.
- **6.5.2. Selection/recruitment of children.** Children in 4th and 5th grades in participating schools will be identified from school rosters along with their parents, who will be contacted via telephone or in-person at school events by research team for the purposes of informed consent (occurs three months prior to the start of data collection).
- **6.5.3. Selection/recruitment of parent.** To maintain statistical independence, only one adult from each family will be interviewed. Rather than arbitrarily targeting whichever parent happens to answer the phone or is met inperson, we will ask the parent to identify the adult ("parent") in the household ("household" may include relatives) who is most likely to have been the target of the child's dementia-information communications.

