- **6.5.4.** Baseline knowledge assessment in parents. Parents who have given consent will be contacted inperson at school events or by telephone one month later, and a baseline dementia knowledge questionnaire will be administered following a brief health literacy survey (see Section 6.6-6.7 for details). We will assess parental knowledge of key signs and symptoms of dementia and the correct course of action through questions identical to those used for the pre-testing of their children.
- **6.5.5. Randomization to arm.** The data coordinating center has developed randomization algorithms to incorporate rolling enrollment which will be applied as schools will be contacted on a rolling basis over the 5 year study period. The investigators will not be told which arm any given school is assigned until after the baseline assessments have been completed. It is not possible to blind to condition, once intervention has been assigned.
- **6.5.6.** Baseline knowledge assessment in children. Around one month after the baseline knowledge assessment in parents, all participating children in both arms of the trial will attend a session to be held in the school auditorium, during which children's knowledge concerning dementia symptoms and response will be assessed (see Sections 6.6-6.7 for details).
- **6.5.7. Implementation of the intervention/control.** The intervention and control conditions will be implemented immediately following the children's' pretest knowledge assessment. Certified lay health facilitators will conduct the intervention or usual care program in 1-hour sessions, over three consecutive days, in schools assigned to the either the intervention or control arm. An immediate post-test will be administered at the end of the third day to children in both the intervention and control arms.
- **6.5.8. 1-week follow-up data collection (parents).** One week after the completion of the 3-day intervention and control programs, follow-up surveys will be conducted in-person at school or, when that is not possible, by telephone (with a telephone protocol of up to five telephone contact attempts if necessary). These surveys assess: (1) Has the child told parent about participating in OSHH at school and discussed dementia with them? and (2) Does the parent recall *what* the child communicated regarding the symptoms and recommended action? To assess these, the research surveyor will use a structured interview format (See Sections 6.6-6.7).

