6.6. Outcome Measures

- **6.6.1. Dementia Symptom and Response Knowledge Assessment (student).** We will use similar instruments to those in our OSHH pilot study²⁷ to replicate our findings by assessing children's pre- and post-test knowledge of AD symptoms and recommended action. Multiple choice questions will be given to assess knowledge of (1) dementia localization (Where in the body does Alzheimer disease occur?(brain) In which part of the brain does Alzheimer disease happen? (Remembering part) What part of the brain helps you remember? (Hippocampus) (2) Recognition of 6 key signs/symptoms (Forgetting words and familiar faces and names; Losing things all the time; Overlooking chores like paying the bills and cleaning; Writing things down all the time; Having trouble counting out the right amount of money when paying; Having trouble using household appliances like a remote control or microwave) plus two distractors (Chest pains, Facial droop), (3) Response to symptoms presented in a hypothetical scenarios in which the dementia diagnosis is not given (considered normal aging v. concerning for dementia (and needs to be seen by physician), (4) assessment of the FLOW mnemonic, (5) self-efficacy for dementia recognition, and (6) ability to formulate the correct action plan in response to recognizing dementia
- **6.6.2.** Assessment of child's communication to parent about dementia signs/symptoms. This measure assesses whether the child has talked with one of the adults in the household in both the OSHH and control arms concerning symptoms of dementia and correct response.

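### The OSHH comic and song go on the study website with no stated limit by arm, and portal use is not split by arm, so control-family exposure is neither blocked nor measured

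*Combined protocol and SAP*

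**What the plan says.** Section 6.3.1 says the comic is one "which is distributed during the program and made available on our website along with the program's song". The Figure 5 caption says the comic reviews FLOW and contrasts normal with pathologic cognitive aging. The section gives no login, no limit by arm and no posting date. Section 6.5.1.b adds a cartoon, still to be made, built on the same song and characters.

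The only statement about online use is in Section 6.4.b, under program fidelity: "We will also track the use of our online program portal by participants and benchmark this access so that we can monitor it for outliers". It does not say whether the portal is the website that holds the comic, whether use will be compared by arm, or whether it enters any analysis.

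The tested content overlaps with these materials. Section 6.6.1 lists "4) assessment of the FLOW mnemonic", six symptoms, and scenarios separating normal aging from possible dementia. Section 6.5.4 gives parents at baseline "questions identical to those used for the pre-testing of their children". Section 6.6.2 measures child-to-adult communication "in both the OSHH and control arms concerning symptoms of dementia and correct response".

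Section 6.5.8 places the 1-week parent survey after both the intervention and the control programs. Its first listed topic is whether the child told the parent about taking part in OSHH. Section 6.8 takes parent recognition of AD symptoms, after the program and at three months, as the primary aim for power.

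**The concern.** A control family that finds the comic or song receives part of the intervention. Control families have some prompts to look. Parents are questioned on dementia about one month before the program and again at 1 week and 3 months, and the 1-week survey as described would give them the program's name well before the 3-month outcome. Section 6.9 offers the control program to intervention schools once they finish. No section offers OSHH to control schools, so the website is the only route to it that the plan mentions.

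The plan itself treats earlier exposure as a reason to exclude: Section 6.2.2 bars schools that already had OSHH or HHS programming. Leaving access during follow-up undefined sits badly with that rule.

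Exposure of controls would raise their scores on FLOW content and shrink the difference between arms. It would push toward no effect, so it would not create a false positive. With no record of use by arm, however, a null result could not separate an ineffective program from one that controls had partly seen.

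**Working it through.** **1. How far the online material overlaps with the test.** Section 6.6.1 tests six symptoms. Four (forgetting, losing, overlooking chores, writing things down) match the FLOW elements in Section 6.3.1. Two (counting out money, using appliances) are not in the FLOW list; Section 6.3.1 says executive dysfunction is covered through role play. The mnemonic and the normal-versus-concerning scenarios are also tested. Localization is tested but not shown to be in the comic or song. The overlap is substantial but partial.

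**2. How long the exposure window is.** Table 4 has the first school starting in Year 1, Month 7, and the last 3-month visits in Year 5.

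**3. The plan's own power.** Inputs from Sections 6.8.1 and 6.8.2: 400 parents per group, V_if = 1.87, R = 0.70, SD = 1.06, two-sided 0.05, 80% power.
- Effective n per arm = 400 × 0.70 / 1.87 = 149.7.
- ANCOVA with ρ = 0.4 and a₁ = 0: δ = √[2 × (1.96 + 0.8416)² × 1.06² × (1 − 0.4²) / 149.7] = 0.315. This matches Table 2.
- Binary outcome, as a two-proportion test at n = 149.7 and a 16.7-point difference: 84.8%, 82.8% and 83.8% for pre-test rates of 30%, 40% and 50%. Table 3 prints 85.37%, 83.05% and 83.45% (first block, ρ = 0.4). This approximates the plan's repeated-measures formula but lands within 1 point of each printed value.

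**4. Dilution, continuous outcome.** Let c be the share of control parents exposed and f the fraction of the full effect they gain. The difference is multiplied by (1 − c·f), and power = Φ[2.8016 × (1 − c·f) − 1.96]. Neither c nor f is in the documents; all values below are assumed.

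| c | δ seen at f = 1 | Power, f = 1 | Power, f = 0.5 | Power, f = 0.25 |
|---|---|---|---|---|
| 0% | 0.315 | 80% | 80% | 80% |
| 5% | 0.299 | 76% | 78% | 79% |
| 10% | 0.284 | 71% | 76% | 78% |
| 20% | 0.252 | 61% | 71% | 76% |

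Example for c = 10%, f = 1: 2.8016 × 0.90 = 2.5214; Φ(0.5614) = 0.713. The powers depend only on the 80% starting point and the two-sided 0.05 level, so they do not turn on V_if, R or the SD.

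**5. Dilution, binary outcome, f = 1.** The control rate at 3 months becomes the pre-test rate plus c × 16.7 points. For pre-test rates of 30/40/50%, power falls from 85/83/84% to 81/79/80% at c = 5%, 76/74/76% at 10% and 66/64/66% at 20%.

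**6. Whether the plan already allows for this.** It does not. The Table 3 rows with 5 points of control improvement also raise the intervention rate, so the adjusted difference stays fixed: for example 56.7 − 35 − (35 − 30) = 16.7. They do not test a shrinking difference.

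**The case against.** The strongest reply is that this builds on silence. The website sentence sits in the description of the intervention arm. It does not say access is open, when posting happens, or that control families get the address. Section 6.4.b speaks of use by participants, which may mean that users can be identified. Section 6.5.8 lists what the survey covers, not its script, so control parents may never hear the name OSHH. Consent pages are not in the documents, so what families were told is unknown. A comic and a song are also far less than three taught sessions, role play, homework and a booster, so the full-effect figures are a worst case at each exposure rate.

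All of that stands, and it limits the point to an unmanaged risk of unknown size. It does not show that the risk is managed: no section restricts access, and monitoring for outliers is not a comparison by arm.

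A reader might infer more in three ways that the documents do not support.
- That schools were randomized to prevent contamination, so the website defeats the design. No section gives that reason for clustering; teaching by grade in auditoriums explains it as well.
- That the comic and song carry all the tested answers. At least two of the six symptoms lie outside the FLOW list, and the full comic and lyrics are not in the documents.
- That the recruitment video for principals, in which "a specially developed 10-minute explanatory promotional video will explain the OSHH intervention and show the curriculum and program objectives", is a second leak. Principals are not outcome subjects, no route to parent recall is shown, and Section 6.5.1.c says the meetings present both programs.

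**Conclusion.** The point holds as a gap in the plan: as written, control families have a possible route to part of the intervention before the 3-month parent outcome, and the plan neither closes it nor commits to measuring it by arm. Any resulting bias would run toward no effect.

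It would be too strong to say that the effect is diluted. The documents do not show that any control family used the site, and if none does, nothing changes. If 5% to 20% of control parents gained the full effect, power would fall from 80% to between 76% and 61%. At a quarter of the effect, the same exposure leaves 79% to 76%. These figures rest on assumed exposure rates, a normal approximation, and the plan's own 80% as the starting point. The case for acting is the low cost of the remedy and the ambiguity of a null result without exposure data, not a demonstrated loss.

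**What to change.** State in Section 6.3.1 who can open the OSHH pages and when. During the trial, open the comic, song and cartoon pages only with a school access code issued to intervention schools on Day 1. Use a separate code, not the child's 4-digit test ID, so that an identifier linked to test data does not double as a web login. Open the pages to everyone after the last school's 3-month surveys.

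In Section 6.4.b, state whether the portal and the website are the same, and commit to reporting portal use by arm as an exposure measure alongside the primary result.

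Cost: a login on a portal whose use is already tracked, and one added table in the report. The public waits for the materials until follow-up ends, in Year 5 under Table 4. Some intervention families may find the code a nuisance, which could slightly reduce their own use; sending the code home with the comic would limit that.
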